#### Chart Abstraction Form

The study coordinator will abstract information from the medical chart and/or touch base with the clinical team caring for participants to assess clinical outcomes including if the patient has died, been hospitalized or admitted to the emergency department or urgent care, or had recurrence, progression, or death at any time after enrollment and at off study. This form will collect relevant medical information, including dates and diagnoses related to ER visits and hospitalizations, prescription of selective supportive medications, dates of changes and/or discontinuation of cancer treatments, and initiation of hospice services.

#### Provider Satisfaction Survey

The amount of staff effort for PRO-related activities will be assessed based on data completed by the MTOP nurses and physicians involved in managing PRO data. The provider satisfaction survey will be completed at least 6 months from the time the initial participant is enrolled. The study coordinator will ask the providers to complete the form on paper and then immediately upload the results into REDCap or directly enter survey results into REDCap by tablet or computer emailed survey link. The provider survey satisfaction may be repeated during the study duration particularly if changes to the Moovcare® interface or protocol are made.

#### Off-Study Timing and Procedures

Participants are asked to remain on the study completing surveys for 6 months (26 weekly ePROs), or until they go off-study prior to that time. An "Off-study form" requiring information to be abstracted from the participant's medical record will be completed by the study coordinator when the participant goes off study (+ 4-week window for form completion). Consultation with MTOP physician or nurse may be necessary for clarifications of some of the questions in

this form. For example, this form includes information about reasons and timing for the reasons for going off-study. In addition, the final chart abstraction form will also be completed (see above) when going off study. In addition, if a patient goes off study early for any reason other than death, the coordinator will attempt to contact the patient to complete the final Outcomes Questionnaires (including: “Patient Quality of Life” and “Patient Satisfaction”) as soon as possible.

Some of the reasons for patients going off-study include:

- Completion of 6 months (26 weeks) of participation
- Initiation of hospice
- Death
- Moved to a different practice for lung cancer care
- Voluntary disenrollment
- Lost to follow-up
- Removal by principal investigator

#### Incentives

Participants will be informed at the time of recruitment they will be given a \$25 incentive for participation (at enrollment in the Moovcare® portal).

#### **4.4 Expected Risks**

Expected risks for this study are likely minimal and involve psychosocial harms such as emotional distress or embarrassment related to survey questions and breach of confidentiality. Survey questions are similar to questions used in the clinical setting and therefore are unlikely to cause harm. However, should a patient experience emotional distress stemming from these questions, a psychology consult through the Lineberger Comprehensive Cancer Support Program will be obtained. Risk of confidentiality breach will be minimized in several ways as detailed below:

1. Moovcare® is a web-mediated algorithm where patients enter symptom data through a password-secure web platform. Enrolled participants are given a unique password to log on to the site so only they, a caregiver with whom they share the password, and their assigned clinical care team can access their PRO data. Other study data including outcomes questionnaires and chart abstraction forms will be collected through the University of North Carolina (UNC) REDCap web-based platform for secure survey administration.
2. The REDCap system is a secure, HIPAA-compliant web-based application to support distributed data collection governed by standard University, School of Medicine, and Federal information security policies and standards. The REDCap application is hosted and monitored on a secure server located within the UNC CTSA-funded NC TraCS Institute’s Bioinformatics Core. Access to the REDCap database for this study will be restricted to authorized research team members as needed to perform their job functions. Research staff who access the REDCap system will use a unique user ID

provided by the Bioinformatics Core. Each time research staff access REDCap, a unique username and password (login) is required, and REDCap maintains an audit trail of all activity.

3. Strict confidentiality will be maintained. Hard-copy research data will be minimal and stored in locked, secure areas accessible only by the study team. Research data will be maintained in separate charts and identified by ID number only when possible. A master list connecting names and ID numbers will be kept in a separate, secure location. Only IRB-approved members of the research team will have access to secured files and will be educated regarding the protection of patients' rights to confidentiality. At study completion, when the database has been declared to be complete and accurate, the database will be locked.
4. Data transmitted between the server and end-users are encrypted using SSL, and all databases are encrypted. Only study team members will have access to data stored in REDCap, and they will use their UNC ONYEN to gain access. Research team members will be instructed to keep all participant data and patient participation confidential.
5. Approaching patients about enrollment in the clinic poses a risk to privacy. We anticipate this risk to be low. To avoid threats of coercion, providers will be educated but not directly involved with recruitment of patients.

#### 4.5 Removal of Patients from Protocol

Patients will be removed from the study if:

- they experience significant emotional distress in response to mobile remote monitoring
- they indicate that they no longer wish to participate

### 5.0 TIME AND EVENTS TABLE

#### 5.1 Time and Events Table

The study procedures by each study timepoint are detailed below:

##### Enrollment/Baseline Visit

At this time, the following procedures will be performed:

- In person/telephone recruitment and consent
- Registration and training on Moovcare®
- Patient Demographic Form
- Quality Life Surveys and Patient satisfaction survey (*if in person recruitment and/or enrollment, the participant will complete their baseline survey assessment in a private area of the clinic with study coordinator assistance*)

##### Weekly (0-6 months as needed)

At this time, the following procedures will be performed:

- Moovcare® ePRO symptom survey

Month 3, 6/off study

At this time, the following procedures will be performed:

- Patient Quality of Life Survey

Month 6/off study

At this time, the following procedures will be performed:

- Patient Satisfaction Survey

Medical chart abstraction will be conducted at any time after enrollment and at off study.

**Schedule of Activities:**

Study Procedures	- 4 week window		
	Baseline	Month 3	Month 6/Off-study
Informed Consent	X		
Eligibility Criteria	X		
Participant Demographics	X		
Moovcare® Registration and Training	X		
EORTC-QLQ-C30	X	X	X
EORTC-QLQ-LC13	X	X	X
Weekly Moovcare® ePRO symptom survey *	→		
Patient Satisfaction Survey	X		X
Provider Satisfaction Survey			X

\*Participants may also complete the Moovcare® ePRO symptom survey on an as needed basis

**Survey Frequency and Duration:**

Survey	Frequency	Completion Time
Patient Satisfaction Survey	2	3 minutes
EORTC QLQ-C30 survey	3	10 minutes
EORTC QLQ-LC13 survey	3	4 minutes
Weekly Symptom Survey	26	7 minutes
Patient – Initiated Symptom Survey	As needed	7 minutes

**6.0 UNANTICIPATED PROBLEMS**

## 6.1 Definition

As defined by UNC's IRB, unanticipated problems involving risks to study subjects or others (UPIRSO) refers to any incident, experience, or outcome that:

- Is unexpected (in terms of nature, severity, or frequency) given (a) the research procedures that are described in the protocol-related documents, such as the IRB-approved research protocol and informed consent document; and (b) the characteristics of the subject population being studied; Is related or possibly related to a subject's participation in the research; and
- Suggests that the research places subjects or others at a greater risk of harm (including physical, psychological, economic, or social harm) related to the research than was previously known or recognized.

## 6.2 Reporting

Any UPIRSO that occurs during the conduct of this study and that meets all three criteria listed in 6.1 must be reported to the UNC IRB using the IRB's web-based reporting system.

# 7.0 STATISTICAL CONSIDERATIONS

## 7.1 Study Design

This is a nonrandomized, single-center, interventional study. The project will prospectively enroll eligible lung cancer patients undergoing outpatient treatments to a single arm entailing monitoring with weekly patient-reported outcomes surveys linked to automated provider reporting. Outcomes will be measured serially over the course of the study using surveys and chart abstraction.

The primary objective of this study is to evaluate feasibility, acceptability, and adherence with survey completion at the patient level. Secondary objectives include estimating the overall survival and change in quality of life in patients using Moovcare®.

## 7.2 Sample Size and Accrual

The primary objective is to estimate the percentage of available surveys completed by eligible, enrolled patients. Based on other PRO studies including at UNC, approximately 80% of assigned surveys are completed per patient.

The Multidisciplinary Thoracic Oncology Program (MTOP) at the UNC Lineberger Comprehensive Cancer Center sees a patient population representation of the state of North Carolina including approximately 20% African American and 60% female patients. An estimated 600 patients with lung cancer diagnoses are seen each year. Based on other studies on PROs at UNC institutions, it is estimated that 50% of patients meeting screening criteria will be otherwise eligible and enroll. It will take an anticipated 12 months to enroll the target of 50 patients.

### 7.3 Data Analysis Plans

Primary data analysis will include the average per patient survey completion rate, change in quality of life, and patient satisfaction at 6 months.

Descriptive statistics will be provided for patient and provider satisfaction scores. Overall survival will be calculated using the Kaplan Meier method, with time starting at enrollment, and ending at last contact or date of death.

[figure not shown]
Changes in HRQOL, as measured by the EORTC-QLQC30, from baseline to 6 months will be calculated and tested using a paired t-test. Sensitivity analyses will be done using last observation carried forward from 3 months if the 6-month surveys is not answered. If a patient dies before the endpoint of 6 months, they will not be included in these estimates. Longitudinal modeling, including all data over the year, will also be explored to further investigate changes over time.

Exploratory Analyses:

Exploratory data analysis will include comparison of demographics of participants completing most (>75%) of the PRO surveys to those not completing most of the PRO surveys using Chi-squared tests for categorical variables and t-tests for continuous variables. Additional comparisons will be done of available demographics of patients (self-reported or obtainable with a limited HIPAA authorization waiver by the IRB) who refuse enrollment and ineligible patients due to key inclusion criteria such as access to email compared to enrolled patients.

Survival curves will be compared for patients with varying levels of PRO survey compliance (no surveys, >=1 survey, >=75% surveys completed) using a landmark analysis based on the first month and adjusted for demographics and comorbidities. The Kaplan Meier method, along with Cox proportional hazard modeling will be used for this analysis.

Additional exploratory analyses will include [REDACTED]

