#### 4.2 Duration of Study

This study will last for approximately 2 years. Training of providers will take place prior to enrollment starts. Approximately 50 participants will be enrolled over 1 year. Each participants' participation in the study will last up to 6 months or until the patient comes off-study due to transition to hospice, death, or withdrawal from the study. Study analysis of participant data will take place throughout the study duration and at the conclusion.

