#### Outcome Surveys

At enrollment, all participants will be trained by the study coordinator how to use the UNC REDCap online system to complete outcomes surveys for the trial. The outcomes surveys will be completed by all participants at baseline; HRQOL will be reassessed at months 3, 6/off-study (+/- 4 weeks each) and patient satisfaction at 6 months/off-study (+/-4 weeks). Participants will be given a choice to complete from home electronically, or if necessary, in clinic at otherwise scheduled routine follow-up visits which occur at least every 3 months or via phone call (with the study coordinator entering the data after participant paper completion into REDCap). For home electronic completion, the outcomes surveys will be sent when due by email via REDCap. The REDCap will send automatic reminders for incomplete surveys. If the patient does not self-complete this information, the study coordinator also has the option to call or email them to collect the information and then enter it into REDCap. If the patient goes off study prior to week 26, the study coordinator will contact the patient as soon as possible to get the off-study surveys completed.

The patient outcomes surveys include:

- **Participant Demographics Form:** This form asks participants about their baseline information including full name and date of birth and will be administered at the time of enrollment.
- **Quality of Life Questionnaires:** Health-related quality of life will be

assessed by items from the *European Organisation for Research and Treatment of Cancer* Quality of Life Questionnaire Comprehensive 30 (EORTC-QLQ-C30) and Quality of Life Questionnaire Lung Cancer 13 module (EORTC-QLQ-LC13), which will be administered to each patient participant at baseline, months 3, 6/off- study (+/- 4 weeks each). The EORTC is a well-established and frequently used questionnaire that includes a 5-item physical functioning domain, individual symptom items including symptoms specific to lung cancer patients, and a composite quality of life score.

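### The main 6-month quality-of-life estimate omits living patients with no month 6 score; a three-visit repeated-measures model, now only exploratory and tied to a year of data, should replace it

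*Combined protocol and SAP*

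**What the plan says.** Section 2.2.1 lists change in the EORTC scores from baseline at 6 months as secondary endpoint 2. Section 7.3 (Data Analysis Plans) then gives four rules.

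- Main analysis: "Changes in HRQOL, as measured by the EORTC-QLQC30, from baseline to 6 months will be calculated and tested using a paired t-test".
- Missing month 6 form: "Sensitivity analyses will be done using last observation carried forward from 3 months if the 6-month surveys is not answered".
- Deaths: "If a patient dies before the endpoint of 6 months, they will not be included in these estimates".
- Longitudinal model: "Longitudinal modeling, including all data over the year, will also be explored to further investigate changes over time". No model form, covariance structure or missing-data assumption is given.

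On timing, section 4.2 says "Each participants' participation in the study will last up to 6 months". The Outcome Surveys part of section 4.3 says "HRQOL will be reassessed at months 3, 6/off-study (+/- 4 weeks each". The survey table in section 5.1 counts three administrations of each EORTC questionnaire. Section 4.3 also has the coordinator seek a final questionnaire from patients who leave early for reasons other than death, but no section says whether that form counts as the 6-month value.

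**The concern.** A paired t-test needs both scores. A living patient with baseline and month 3 scores but no month 6 score contributes nothing to the main estimate, which is then valid only if such patients changed as the others did. Any stage of lung cancer is eligible, and section 4.3 names hospice, withdrawal, loss to follow-up and a move to another practice as ways off study. Non-response that follows a decline is therefore plausible.

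The method that handles this with data already being collected is in the plan, but it is unspecified, has exploratory status and is tied to the wrong time span. Section 1.3 says the study should supply preliminary data for later controlled studies of quality-of-life outcomes, so an understated decline would carry into their planning.

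**Working it through.** **Schedule check.** Assessments at months 0, 3 and 6 make 3, which agrees with the survey table in section 5.1. A year at 3-month spacing would need 5 (0, 3, 6, 9, 12). No participant has the last two.

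**When the complete-case mean is biased.** Let Y0, Y3 and Y6 be the scores, with common SD s and correlations r03, r06 and r36, and let D = Y6 - Y0. The complete-case mean of D shifts when non-response is driven by something correlated with D:

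- Driver is the month 3 change: cov(D, Y3 - Y0) = s²(r36 - r06 - r03 + 1).
- Driver is the month 3 level: cov(D, Y3) = s²(r36 - r03).

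The documents give no SD, correlation, survival or missing-form rate, so the inputs are assumptions: 43 patients alive at 6 months, means 60/58/55 (higher is better, true change -5), s = 22, r03 = r36 = 0.60, r06 = 0.54. The first covariance is 484 × (0.60 - 0.54 - 0.60 + 1) = 484 × 0.46 = 222.6, so there is bias. The second is 484 × 0 = 0, so there is none.

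**Simulation with these inputs.** There were 6,000 trials per setting. About 24% to 27% of month 6 forms are missing, with probability logistic in the standardised month 3 change (slope 0, 0.5 or 1.0). The likelihood estimate is computed by regressing month 6 on baseline and month 3, which is equivalent for this missing pattern.

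| Non-response | Complete-case | LOCF | Likelihood | SE, complete-case vs likelihood |
|---|---|---|---|---|
| Unrelated to scores | -5.0 | -4.3 | -5.0 | 3.73 vs 3.57 |
| Follows month 3 decline, moderate | -3.8 | about -5.0 | about -5.1 | 3.64 vs 3.54 |
| Follows month 3 decline, strong | about -2.5 | -5.6 | about -5.0 | 3.71 vs 3.76 |

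Two entries can be checked by hand. With 25% missing at random, LOCF gives 0.75 × (-5) + 0.25 × (-2) = -4.25. The SD of D is 22 × √(2 × 0.46) = 21.1, and with 43 × 0.75 = 32.25 pairs the SE is 21.1/√32.25 = 3.7.

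When non-response follows the month 3 level instead, the complete-case mean lies between -4.7 and -5.3 across three assumed correlation sets.

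**Range over the missing rate.** A second set of assumptions uses SD 20, means 60/57/54 (true change -6), three correlation structures, and non-response following the month 3 change:

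| Month 6 missing | Complete-case | LOCF | Likelihood |
|---|---|---|---|
| 10% | -4.8 to -5.4 | -6.0 to -6.5 | about -6.0 |
| 20% | -3.7 to -4.9 | -5.8 to -6.8 | about -6.0 |
| 30% | -2.6 to -4.4 | -5.7 to -6.9 | about -6.0 |
| 40% | -1.6 to -3.9 | -5.5 to -6.8 | about -6.0 |

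With non-response following only the month 3 level, complete-case stays at -5.99 to -6.06.

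**The case against.** The strongest reply is that the plan already has a safeguard. The LOCF analysis uses the month 3 scores of exactly these patients and, where non-response follows decline, it lies closer to the truth than the t-test does. A reader might infer that those month 3 scores are used nowhere; the documents do not support that. What remains is that LOCF is only a sensitivity analysis and assumes no change after month 3. Its error changes direction with the mechanism: -4.3 in one setting and -5.6 in another, against -5.

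A reader might also infer that the longitudinal model cannot be run. It can, on the three planned visits. The amendment summary says section 7.3 was updated to remove time points after 6 months, so the reference to a year is probably leftover wording. It needs correcting but is not evidence of an unworkable analysis.

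Third, the missing rate is unknown. Reminders, coordinator calls, completion in clinic or by phone, and off-study forms may keep it low. That is fair. But the plan does not say whether an off-study form stands in for month 6, so the number omitted cannot be determined from the text.

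Finally, this is a single-arm feasibility study of about 50 patients with no decision rule on HRQOL. The bias is 5 - 3.8 = 1.2 to 5 - 2.5 = 2.5 points, or about 0.3 to 0.7 of a standard error (1.2/3.64 and 2.5/3.71). This limits the weight of the point but does not remove it.

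**Conclusion.** The point holds as a minor-to-moderate improvement to a secondary endpoint. The t-test omits living patients without a month 6 score, and the better model is unspecified, exploratory and given a time span that does not match the schedule.

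It would go too far to conclude that the HRQOL result will be biased. That depends on why forms are missing, which the documents cannot settle. The understatement of 1.2 to 2.5 points rests on the assumed means, SD and correlations, on about 25% missing, and on non-response following a month 3 decline. The case for the model is that it is about unbiased in every setting examined and costs essentially no precision. It remains unbiased only if non-response depends on scores already observed.

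**What to change.** In section 7.3:

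1. Replace the reference to a year with baseline, month 3 and month 6/off-study.
2. Make the main estimate of 6-month change a mixed model for repeated measures on these three visits, with visit as a category and an unstructured covariance. Exclude patients who die before 6 months, as the section already states. Report the mean change with a 95% CI.
3. Keep the paired t-test in patients with both forms as supplementary. Keep LOCF, if retained, as a sensitivity analysis.
4. Assign an off-study form to the visit whose window contains it, so that an early form is not counted as a month 6 value. Taking month 3 as week 13 and month 6 as week 26, the 4-week windows are weeks 9 to 17 and 22 to 30. The text should also say what happens to a form outside both.

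The cost is SAP wording and one standard model, with no new data. The downside is an analysis slightly less simple than a t-test.

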## 3.0 PATIENT ELIGIBILITY

### 3.1 Inclusion Criteria

Patients participating in the study must meet the following inclusion criteria at baseline:

- 3.1.1 18 years or older
- 3.1.2 Diagnosis of lung cancer (any histology, any stage) undergoing outpatient treatment and/or surveillance/monitoring at UNC.

*This may include stage I and II patients who have completed lung resection and/or are undergoing radiation, stage II and III patients receiving neoadjuvant, adjuvant, or definitive chemotherapy, stage IV patients undergoing active therapy or monitoring, patients undergoing surveillance for treated or untreated stage I-III lung cancer, and both limited and extensive small cell lung cancer. The study team will request confirmation of the lung cancer diagnosis from the managing clinician. Patients can be enrolled at any point in their lung cancer treatment trajectory (i.e., not just at initiation of first-line treatment) after a diagnosis of lung cancer has been assigned by the treating clinician. This may include patients assigned a diagnosis of lung cancer without a tissue diagnosis.*

- 3.1.3 Speaks and understands English
- 3.1.4 Reliable access to the internet and email
- 3.1.5 Access to a mobile phone (or device that can receive text messages for registration)

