##### Screening, Recruitment, and Enrollment

Potentially eligible patients will be identified from the review of the visit reason from the thoracic oncology providers' Epic clinic schedules. Patients who have appointments for outpatient care at Multidisciplinary Thoracic Oncology Program (postoperative clinic visit, any radiation, or oncology visit) will be considered. To identify potentially eligible patients, the study coordinator can review clinical documentation such as the patient's chart in the electronic medical record, clinical schedules, or ask clinical staff about potential eligible patients through a limited HIPAA waiver from the IRB. Providers will also be approached by the study coordinator to identify any other patients with lung cancer.

Identified patients will be entered into a screening log. Providers will be asked to verify a clinical diagnosis of lung cancer. For surgical patients, lack of enrollment in concurrent LCCC protocol #1945 will be verified with the assigned study coordinator. Patients meeting the eligibility criteria on the initial screening will be approached in person, by telephone by the study coordinator to verify the remainder of the eligibility criteria and invite the patient to the study. Interested patients will undergo informed consent procedures. An IRB-approved study team member will approach the patient to discuss study procedures, benefits, risks and obtain informed consent prior to any study procedures. Patients who agree to participate will review and sign the informed consent form after the study is explained and questions have been answered.

Patients who are found to be ineligible during screening due to lack of email, phone number, or English language or those potentially eligible during screening but found to be ineligible after contact will be excluded from the study. The reasons for exclusion as well as basic demographics available in the EMR (e.g. race, ethnicity, age, gender, education level if available) will be collected in REDCap.

For patients who are eligible but refuse enrollment, reasons for refusal, as well as basic demographics available in the EMR (e.g. race, ethnicity, age, gender, education level if available) will also be collected within REDCap.

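### The exploratory first-month landmark comparison of survival by survey compliance is adjusted for demographics and comorbidities but not for cancer stage, so its adjusted hazard ratio could reflect stage

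*Combined protocol and SAP*

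**What the plan says.** Under Exploratory Analyses, section 7.3 compares survival between groups defined by how many surveys patients completed: "no surveys, >=1 survey, >=75% surveys completed) using a landmark analysis based on the first month and adjusted for demographics and comorbidities". Kaplan-Meier curves and a Cox model are to be used. No visible text adds stage to this model, stratifies by it or restricts the analysis by it.

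Eligibility is wide. Section 3.1.2 requires: "Diagnosis of lung cancer (any histology, any stage) undergoing outpatient treatment and/or surveillance/monitoring at UNC". It adds: "Patients can be enrolled at any point in their lung cancer treatment trajectory". The examples there run from resected stage I disease to stage IV on active therapy, and include limited and extensive small cell disease.

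On data collection, section 4.3 (Chart Abstraction Form) says: "This form will collect relevant medical information, including dates and diagnoses related to ER visits and hospitalizations". The items listed include neither stage nor comorbidities, but the list is introduced as open.

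On expected compliance, section 7.2 gives a single overall figure: "approximately 80% of assigned surveys are completed per patient". It is not broken down by stage.

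**The concern.** Stage is a main determinant of survival in lung cancer, and this population spans the whole range. The plan already accepts that compliance groups may differ in prognosis, because it adjusts for other patient characteristics. The visible list leaves out the extent of the disease under study.

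A common cause of both compliance and survival produces an association between them even when neither affects the other. If patients with advanced disease complete fewer surveys, low compliance will look harmful. If they complete more, perhaps because they are seen more often, low compliance will look protective.

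What is at stake is how the result is read. Section 1.3 says the study should supply preliminary data for later controlled studies. A hazard ratio labelled as adjusted, but not for stage, could be given more weight in that planning than it deserves.

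**Working it through.** The plan states no effect size, event count or power for this analysis, so there is no figure to reproduce. The check is a comparison of the text, then an illustration of possible size.

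**Text.** Stage is unrestricted at entry (section 3.1.2). The adjustment is for demographics and comorbidities (section 7.3). Stage describes the index cancer, so neither term would ordinarily cover it. The landmark deals with immortal time, since patients must survive the first month to be classified. It does not balance baseline prognosis between the groups.

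**Inputs.**
- From the documents: 50 patients (section 7.2).
- Assumed: stage IV share *s* of 30, 40 or 50%; 6-month mortality of 3 or 5% in earlier stages and 25 or 35% in stage IV; the proportion reaching at least 75% completion, by stage, as given below; and no compliance effect within stage.

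**Formula.** Among high compliers the stage IV share is *s·p*(IV) / [*s·p*(IV) + (1−*s*)·*p*(earlier)], where *p* is the proportion reaching 75%. Among low compliers, *p* is replaced by 1−*p*. Mortality *d* in each group is the weighted mean of the two stage-specific mortalities. The stage-unadjusted hazard ratio, low versus high compliance, is approximately log(1−*d*low) / log(1−*d*high).

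**Stage IV complies less** (85% earlier; 65 or 70% stage IV).
- Largest: *s* = 30%, mortality 3%/35%, compliance 85%/65%. High compliers: 0.195/(0.195+0.595) = 24.7% stage IV, mortality 0.109. Low compliers: 0.105/(0.105+0.105) = 50.0%, mortality 0.190. HR = log(0.810)/log(0.891) = 1.83.
- Smallest: *s* = 50%, mortality 5%/25%, compliance 85%/70%. Stage IV shares 45.2% and 66.7%, mortality 0.140 and 0.183. HR = 1.34.

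**Equal compliance by stage.** The stage mix is the same in both groups, so HR = 1.0.

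**Stage IV complies more** (65 or 70% earlier; 85% stage IV).
- Furthest from 1: *s* = 30%, mortality 3%/35%, compliance 65%/85%. Mortality is 0.145 in high and 0.080 in low compliers. HR = 0.53.
- Nearest to 1: *s* = 50%, mortality 5%/25%, compliance 70%/85%. Mortality is 0.160 and 0.117. HR = 0.71.

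Within stage the hazard ratio is 1.0 in every case, by construction.

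**Precision.** With constant hazards, expected deaths between months 1 and 6 are 50 × Σ share × [(1−*m*)^(1/6) − (1−*m*)], where *m* is 6-month mortality.
- Low setting (30% stage IV, mortality 3%/25%): 0.87 + 3.05 = 3.9.
- High setting (50% stage IV, mortality 5%/35%): 1.04 + 7.02 = 8.1.

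Assuming 80% of patients are high compliers, SE(log HR) = 1/√(deaths × 0.8 × 0.2). This is 1.26 and 0.88, so the 95% limits lie a factor of about 11.9 and 5.6 either side of the estimate. The largest confounding above is |log 0.53| = 0.63 on the log scale, below the smaller standard error.

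**The case against.** The strongest reply is that little depends on this analysis. It is exploratory, has no decision rule and feeds no primary or secondary endpoint. With about 4 to 8 deaths to month 6 the interval would swamp any plausible confounding, so adding stage would rarely change a conclusion. That stands, and it sets the severity. Nor would stage remove all confounding: treatment phase and histology are just as open at entry. That also stands, and is why the result needs a non-causal label even after the change.

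It could be said that the covariates might be in redacted text. The redaction in section 7.3 introduces additional analyses after this model has been fully described, so it probably does not hide them. The point is still limited to visible text.

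Some stronger readings are tempting but not supported:
- *Compliance and survival will be confounded, in a known direction.* No compliance or mortality by stage is given. The illustration runs both ways and includes no effect.
- *Stage is not collected.* The abstraction list is open, so this cannot be judged, and nothing visible prevents stage from being added.
- *The planned covariates would crowd stage out or make the model fail.* Section 7.3 fixes no number of terms. The itemised demographics in section 4.3 ("basic demographics available in the EMR (e.g. race, ethnicity, age, gender, education level if available") are examples collected on ineligible and refusing patients, not a covariate list for this model.
- *The compliance groups are ill defined.* Literally, at least one survey includes at least 75%, but the ordered reading is natural. That is an editorial matter.

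**Conclusion.** The point holds as a minor one. As written, the plan would report an adjusted hazard ratio for compliance that leaves out stage, in a population where stage is unrestricted. Whether this distorts the estimate depends on compliance differing by stage, which the documents do not show either way. The ranges of 1.34 to 1.83 and 0.53 to 0.71 rest on assumed stage mix, mortality and compliance by stage. They show that distortion is possible in either direction, not that it is expected or how large it would be.

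The death count assumes follow-up to month 6. Section 4.3 ties the last abstraction to leaving the study ("the final chart abstraction form will also be completed (see above) when going off study"), although it also allows abstraction at any time after enrolment. Longer follow-up would add deaths and precision but would not remove confounding by stage.

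**What to change.** In section 7.3, add stage at enrolment to this Cox model as a stratum or covariate, in two levels: I-III or limited versus IV or extensive. Make sure stage at enrolment is on the chart abstraction form. State that the comparison is descriptive and that a compliance-survival association is not to be read as causal.

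The cost is one or two sentences of analysis text, one more chart item per patient, and slightly less precision in an analysis that already has few deaths.
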